## 9.6 Statistical Methods

This section describes the statistical methods that address the primary and secondary objectives. Methods related to exploratory endpoints will be described in the sSAP.

# 9.6.1 Statistical Methods for Efficacy Analysis

The statistical methods for efficacy analyses will be documented in the sSAP.

ORR will be estimated using an exact method based on the binomial distribution (Clopper-Pearson interval).

## 9.6.2 Statistical Methods for Safety Analysis

Safety and tolerability will be assessed by clinical review of all relevant parameters including AEs, SAEs, laboratory tests, vital signs, ECG measurements, and physical examinations.

AEs will be summarized by counts and frequencies for each dose level. Laboratory tests, vital signs, and other safety endpoints will be summarized as appropriate.

DLTs will be listed and summarized by dose level. The pool-adjacent-violators algorithm [Ji Y, Li Y, Bekele BN 2007], which forces the DLT rate estimates to be nondecreasing with increasing dose levels and pools adjacent violators for weighted estimates by sample size, will be used to estimate the DLT rates across doses in each treatment arm. The estimate of the DLT rate among participants treated at the RP2D and the 90% Bayesian credible interval based on a prior distribution of Beta (1,1) for the estimate will be provided.

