## 3 HYPOTHESES, OBJECTIVES, AND ENDPOINTS

In male and female participants with advanced/metastatic solid tumors:

Objectives	Endpoints
Primary	
To determine the safety and tolerability and to establish a preliminary maximum tolerated dose/recommended Phase 2 dose of MK-1088 administered as monotherapy and in combination with pembrolizumab infusion in Part 1	
 
Dose-limiting toxicity (DLT)
 
Adverse events (AE)
 
Discontinuing study intervention due to an AE
 

Secondary	
To evaluate the PK of MK-1088 administered as monotherapy and in combination with pembrolizumab infusion in Part 1 and in Part 2	- PK parameters including AUC and $$C_{\rm max}$$
To evaluate the antitumor activity (objective response rate [ORR] based on PCWG-modified RECIST 1.1 [prostate cancer participants only] or RECIST 1.1 [all other participants]) of MK-1088 as assessed by the investigator when used as monotherapy and in combination with pembrolizumab in Part 1 and in Part 2	Objective response (OR) is a complete response (CR) or partial response (PR)

Objectives	Endpoints
Tertiary/Exploratory	
To evaluate progression-free survival (PFS) and overall survival (OS) of participants treated with MK-1088 both as monotherapy and in combination with pembrolizumab. In solid tumors, assessment will be based on RECIST 1.1 as assessed by the investigator.  Metastatic prostate cancer response assessments will also use PCWG criteria.	
 
PFS: the time from treatment allocation to the first documented disease progression or death due to any cause, whichever is first
 
OS: The time from treatment allocation to death due to any cause
 

To evaluate the duration of response (DOR) per RECIST 1.1 as assessed by the investigator	DOR is defined as the time from the first documented evidence of CR or PR until progressive disease (PD) or death due to any cause, whichever occurs first, in participants demonstrating PR or CR
To identify molecular (genomic, metabolic and/or proteomic) biomarkers that may be indicative of clinical response/resistance, safety, pharmacodynamic activity, and/or the mechanism of action of MK-1088 as monotherapy and in combination with pembrolizumab	Molecular (genomic, metabolic and/or proteomic) determinants of response or resistance to treatments, using blood and/or tumor tissue

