Participants will be initially enrolled to receive MK-1088 in monotherapy (Arm 1). Enrollment in Arm 1 (MK-1088 in monotherapy) at DL2 will begin once all participants complete Cycle 1 at DL1 of Arm 1 and a dose-escalation decision has been made. Enrollment in Arm 2 (MK-1088 in combination with pembrolizumab) at DL1 may begin after all participants complete Cycle 1 at DL1 of Arm 1 and a dose-escalation decision has been made. Thus, the starting dose of MK-1088 in the combination arm will be at least 1 level below the dose level being tested concurrently in the MK-1088 monotherapy arm. The final number of participants enrolled in Part 1 will depend on the empirical safety observations (DLT), and what dose is ultimately identified as the RP2D using the adjusted mTPI design.

Based on the adjusted mTPI design, it is anticipated that data from 14 participants at a dose level will provide sufficient data to declare an MTD or RP2D. However, should there be clinical PK or safety reasons, additional participants and/or dose levels may be evaluated. The pool-adjacent-violators algorithm [Ji Y, Li Y, Bekele BN 2007] will be used to estimate the DLT rates across doses in each treatment arm under the assumption of monotonicity between DLT rates and dose levels. The dose with an estimated DLT rate closest to 30% may be treated as a preliminary RP2D. The totality of the data will be considered before deciding on the dose(s) to carry forward to Part 2. The RP2D of MK-1088 in the combination arm (Arm 2) may equal, but will not exceed, the RP2D in the MK-1088 monotherapy arm (Arm 1).

In Part 2, safety and efficacy of MK-1088 in combination with pembrolizumab at the RP2D defined in Part 1 Arm 2 will be assessed. At least 3 indication-specific expansion cohorts are planned based on evolving data and will be incorporated into an amendment before initiating Part 2. Additional lower and/or higher doses of MK-1088 in combination with pembrolizumab may also be explored in Part 2. The final RP2D for future studies will be confirmed using all available safety information (including early and late toxicities from

PRODUCT: MK-1088
PROTOCOL/AMENDMENT NO.: 002-01

Parts 1 and 2), as well as PK and pharmacodynamic data, and preliminary efficacy assessments.

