A D or DU decision at the lowest dose level will stop the study. An E decision at the highest dose level will result in staying at that level. During dose-finding, it may be acceptable to deescalate to an intermediate dose that was not predefined and not previously studied if evaluation of toxicity at such a dose is desired. If this approach is taken, 3 to 6 new participants may be enrolled at the new intermediate dose, and the aforementioned rules should be used to determine further enrollment at this dose level.

After 14 participants have been enrolled at any of the tested doses (including intermediate doses), dose-finding will stop if the mTPI table indicates "S" for staying at current dose. Otherwise, up to 14 new participants may be enrolled at a lower dose if "D" or "DU" is indicated, or at a higher dose if "E" is indicated.

The pool-adjacent-violators algorithm [Ji Y, Li Y, Bekele BN 2007] will be used to estimate the DLT rates across doses. The dose with an estimated DLT rate closest to 30% will be treated as a preliminary MTD. However, the totality of the data will be considered before deciding on the dose(s) to carry forward to Part 2. The dose-escalation schedule may be adjusted based on pharmacodynamic, PK, and safety data emerging throughout the study. The preliminary RP2D of MK-1088 in the combination arm (Arm 2) will not exceed, but may be equal to, the preliminary RP2D in the MK-1088 monotherapy arm (Arm 1).

Note that although 30% was the target toxicity rate used to generate the guidelines in Table 3, the observed rates of participants with DLTs at the MTD may be slightly above or below 30%). When selecting the RP2D of the monotherapy and combination therapy, the totality of the safety data (eg, duration, reversibility, severity, and nature of the DLTs and AEs) will be evaluated.

PRODUCT: MK-1088

PROTOCOL/AMENDMENT NO.: 002-01

Table 3 Dose-finding Rules per Adjusted mTPI Design

	Num	Number of Participants Evaluable for DLT at Current Dose										
Number of												
participants with at												
least 1 DLT	3	4	5	6	7	8	9	10	11	12	13	14
0	Е	Е	Е	Е	Е	Е	Е	Е	Е	Е	Е	Е
1	S	S	S	Е	Е	Е	Е	Е	Е	Е	Е	Е
2	D	D	S	S	S	S	S	S	Е	Е	Е	Е
3	DU	DU	D	D	D	S	S	S	S	S	S	S
4		DU	DU	DU	D	D	D	D	S	S	S	S
5			DU	DU	DU	DU	DU	D	D	D	D	S
6				DU	DU	DU	DU	DU	DU	D	D	D
7					DU	D						
8						DU						
9							DU	DU	DU	DU	DU	DU
10								DU	DU	DU	DU	DU
11									DU	DU	DU	DU
12										DU	DU	DU
13											DU	DU
14												DU

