the 21-day DLT observation period of the previous dose cohort is completed and a dose-escalation decision is made.

When Part 2 is open for enrollment, IVRS will allocate participants by tumor type.

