# 9.4.2 Safety Endpoints

The primary safety endpoint is the incidence of DLTs. In addition, safety and tolerability will be assessed by clinical review of all relevant parameters including AEs, laboratory tests, and vital signs.

A description of safety measures is provided in Section 8.3.

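### At the RP2D data cut, crude AE frequencies by dose level are likely to understate post-Cycle 1 toxicity at the newest, highest doses; common-window and per-exposure summaries are needed beside them

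*Combined protocol and SAP*

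**What the plan says.** Section 3 lists three primary endpoints: DLT, AEs, and discontinuation of study intervention due to an AE. Section 9.4.2 narrows the emphasis: "The primary safety endpoint is the incidence of DLTs".

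For AEs, the tabulation given in Section 9.6.2 is: "AEs will be summarized by counts and frequencies for each dose level". It names no analysis for discontinuation due to an AE. Section 9.1 adds only summary statistics where appropriate. The supplemental SAP is reserved for exploratory and other nonconfirmatory analyses, so it is not a promised home for a fuller AE analysis.

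Four other parts of the plan bear on this:

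- **Sequence.** Section 4.1: "Enrollment in Arm 1 (MK-1088 in monotherapy) at DL2 will begin once all participants complete Cycle 1 at DL1 of Arm 1". Section 6.3.1 opens each new cohort once "the 21-day DLT observation period of the previous dose cohort is completed and a dose-escalation decision is made".
- **Observation time.** Treatment may last up to 35 cycles (Section 4.1), and AEs are reported until 30 days after it stops (Section 8.4.1). Only DLT has a common window, Cycle 1 (Section 6.6.2).
- **Use of AEs.** When the RP2D is selected, "the totality of the safety data (eg, duration, reversibility, severity, and nature of the DLTs and AEs) will be evaluated" (Section 4.3.1.3). Section 4.1 adds: "The final RP2D for future studies will be confirmed using all available safety information", and counts late toxicities among that information.
- **Timing.** Part 2 starts once the Arm 2 RP2D is identified (Section 6.6.3), and data are examined continuously for dose-finding (Section 9.7).

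**The concern.** A crude frequency is the share of participants with an event over whatever time each has been observed. It compares doses fairly only if observation time is similar. In a sequential escalation that is cut when a dose is chosen, the lowest level has been watched longest and the highest level least, so dose and time at risk are confounded.

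The distortion makes the newest and highest doses look better tolerated than they are. It matters most for toxicity after Day 21, which the DLT rule cannot see. For a drug taken daily over many cycles, AEs and discontinuations due to AEs are the evidence on whether a dose can be sustained.

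**Working it through.** The plan gives no AE rate and no follow-up by dose level, so there is no figure of its own to reproduce.

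**1. Elapsed time from the documents' timings.** Three participants need at least 2 days (24-hour stagger, Section 6.3.1), and a cohort of 3 to 6 may enrol over 7 to 14 days (Section 4.3.1.3). Adding the 21-day window gives 23 to 35 days per level. With five levels and no repeat cohorts, when DL5 completes Cycle 1:

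- DL1: 4 × 23 + 21 = 113 days, to 4 × 35 + 21 = 161 days
- DL5: 21 days

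**2. Model.** These inputs are assumptions, not taken from the documents: constant risk of a first AE of 8% per cycle at DL1 and 16% at DL5; exponential time on treatment with median 9 or 18 weeks. For follow-up of F weeks, with AEs counted on treatment:

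P = λ/(λ+μ) × (1 − exp(−(λ+μ)F)), where λ = −ln(1 − risk)/3 and μ = ln 2/median

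- λ = 0.0278 (8%) or 0.0581 (16%) per week
- μ = 0.0770 (median 9) or 0.0385 (median 18) per week

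**3. Earliest cut: DL5's first cohort has just closed its DLT window.** With 6 weeks per level, mean F is 4 × 6 + 4 = 28 weeks at DL1 and 4 weeks at DL5. For median 9:

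- DL1: 0.0278/0.1048 × (1 − exp(−0.1048 × 28)) = 25%
- DL5: 0.0581/0.1351 × (1 − exp(−0.1351 × 4)) = 18%

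For median 18 the figures are 35% and 19%. The dose with twice the risk shows the lower frequency.

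**4. Cut with DL5 filled to 14.** Sections 4.1 and 4.3.1.3 anticipate 14 participants at a level before an RP2D is declared. Assume k = 3 or 4 equal batches and s = 4 to 6 weeks per step. DL5 batches then have F = 4, 4+s, and so on up to 4+(k−1)s; DL1 has F = 4+(k−1)s+4s. For k = 3 and s = 4, DL5 has F = 4, 8 and 12, and DL1 has F = 28.

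| Median treatment | DL1 crude | DL5 crude | Ratio |
|---|---|---|---|
| 9 weeks | 25-26% | 27-32% | 1.07-1.22 |
| 18 weeks | 35-40% | 31-39% | 0.88-0.98 |

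The true per-cycle risk ratio is 2.

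**5. Adding the 30-day post-treatment period.** Let w = 30/7 weeks. For F ≤ w, P = 1 − exp(−λF). For F > w, with G = F − w:

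P = 1 − exp(−λw) × [μ/(λ+μ) × (1 − exp(−(λ+μ)G)) + exp(−(λ+μ)G)]

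The earliest cut becomes 33-41% against 21%. In the setting of step 4 the ratios are 1.01-1.18 (median 9) and 0.85-0.96 (median 18). The conclusion does not change.

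**6. Full follow-up, equal treatment duration.** As F grows, the step 2 formula tends to λ/(λ+μ): 27% against 43% (median 9) and 42% against 60% (median 18). The order is correct.

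**7. The alternatives on the same inputs.** A Cycle 1 window (F = 3) gives 7-8% against 14-15% at any of these cuts. First events per cycle at risk are −ln(0.92) = 0.083 against −ln(0.84) = 0.174, a ratio of 2.1.

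**The case against.** The strongest reply has five parts.

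- **The dose-finding rule is insulated.** DLTs have a fixed 21-day window and drive both the mTPI table and the pool-adjacent-violators estimate. This stands in full. A reader might infer that escalation or the MTD estimate is biased; the documents do not support that.
- **The earliest cut is not the usual decision point.** This also stands. A reader might infer that the more toxic dose will generally show the lower AE rate. With DL1 at 28 weeks, the reversal in step 3 ends once DL5's mean follow-up reaches about 7 to 9 weeks, and with 14 participants there it is absent or small. If the chosen dose is reached by de-escalation, it is not the newest level. AEs confined to Cycle 1 do not reverse, because every level is observed through Cycle 1.
- **In the final report, enrolment order does no harm.** This stands if treatment duration is equal, since the maximum duration and AE window are the same at every level. If high-dose participants stop sooner, crude rates can still mislead. In a separate model with a monthly hazard of 0.10, doubled at the high dose, median treatment of 6 against 2 months gives 51% against 48%. That is a different mechanism from enrolment order.
- **AEs enter through clinical review, not by ranking percentages.** This is true, and no section says the RP2D is chosen by comparing AE frequencies. Time of onset and duration are recorded, treatment duration is summarized (Section 9.12), and post-crossover events are kept apart (Section 9.5.1). But exposure is not linked to AE counts, and the only AE summary specified for each dose level is the crude one.
- **Small numbers.** The exact 95% interval is 1-91% for 1 of 3 and 4-78% for 2 of 6. Crude frequencies are just as imprecise and carry the bias as well.

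**Conclusion.** The point holds in a limited form. With crude frequencies alone, AEs arising after Cycle 1 and discontinuations due to an AE are unlikely to be comparable between dose levels at the RP2D data cut, and the error favours newer, higher doses. At a realistic cut, with the top level filled to 14, a two-fold risk is shrunk to a crude ratio of about 0.9 to 1.2. The marked reversal belongs to the earliest cut only.

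The size rests on assumed AE risks, constant hazard, assumed time on treatment and assumed batch timing. It was calculated for first AEs; the same reasoning applies to discontinuation due to an AE, which was not modelled separately. Unequal follow-up is an inference from sequential opening and the timing of Part 2. A reader might take it as a stated feature of the plan, but it is not. This is a cheap improvement to a descriptive analysis, not a flaw in the dose-escalation design.

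**What to change.** In Section 9.6.2, by arm and dose level, add:

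- **(a) Common windows.** AEs, Grade 3 or higher AEs, SAEs and discontinuation due to an AE within Cycle 1, and within Cycles 1-3 among participants with the opportunity to complete them by the data cut.
- **(b) Per exposure.** First events per participant-time at risk for the same categories, with the 30-day post-treatment period included in the time at risk for AEs.

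State that these summaries are referred to when AEs are compared between doses for the RP2D, and keep crude frequencies as descriptive. Both are useful: (b) alone leans on a roughly constant hazard, and the Cycle 1 window alone misses later events.

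The cost is SAP wording and a few extra tables from AE onset and dosing dates already collected. The rates will be imprecise at 3 to 14 participants per level, so event counts and time at risk should be shown beside them.

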## 9.6.3 Summaries of Baseline Characteristics, Demographics, and Other Analyses

# 9.6.3.1 Demographic and Baseline Characteristics

Demographic variables, baseline characteristics, primary and secondary diagnoses, and prior and concomitant therapies will be summarized.

PROTOCOL/AMENDMENT NO.: 002-01

# 9.6.3.2 Pharmacokinetic and Pharmacodynamic Modeling Analysis

PK parameters of study interventions will be summarized by planned visit and time for each dose separately.

PK and pharmacodynamics modeling analyses will be documented in the sSAP.

# 9.7 Interim Analyses

No interim analyses are planned. Data will be examined on a continuous basis to allow for dose-finding decisions.

# 9.8 Multiplicity

There will be no multiplicity adjustment since no hypothesis testing will be conducted.

# 9.9 Sample Size and Power Calculations

With a maximum sample size of 14 at each dose level, the overall sample size for this Phase 1/Phase 2 study is expected to be approximately 80. The actual sample size depends on the safety profiles and number of doses studied.

# 9.10 Subgroup Analyses

Subgroup analyses of efficacy endpoints will be documented in the sSAP.

# 9.11 Compliance (Medication Adherence)

Drug accountability data for study intervention will be collected during the study. Any deviation from protocol-directed administration will be reported.

# 9.12 Extent of Exposure

The extent of exposure will be summarized as duration of treatment in cycles.

PROTOCOL/AMENDMENT NO.: 002-01

# 10 SUPPORTING DOCUMENTATION AND OPERATIONAL CONSIDERATIONS

## 10.1 Appendix 1: Regulatory, Ethical, and Study Oversight Considerations

### 10.1.1 Code of Conduct for Clinical Trials

Merck Sharp & Dohme LLC, Rahway, NJ, USA (MSD)

#### Code of Conduct for Interventional Clinical Trials

#### I. Introduction

#### A. Purpose

MSD, through its subsidiaries, conducts clinical trials worldwide to evaluate the safety and effectiveness of our products. As such, we are committed to designing, implementing, conducting, analyzing, and reporting these trials in compliance with the highest ethical and scientific standards. Protection of participants in clinical trials is the overriding concern in the design and conduct of clinical trials. In all cases, MSD clinical trials will be conducted in compliance with local and/or national regulations (including all applicable data protection laws and regulations), and International Council for Harmonisation Good Clinical Practice (ICH-GCP), and also in accordance with the ethical principles that have their origin in the Declaration of Helsinki.

#### B. Scope

Highest ethical and scientific standards shall be endorsed for all clinical interventional investigations sponsored by MSD irrespective of the party (parties) employed for their execution (e.g., contract research organizations, collaborative research efforts). This Code is not intended to apply to trials that are observational in nature, or which are retrospective. Further, this Code does not apply to investigator-initiated trials, which are not under the full control of MSD.

## II. Scientific Issues

### A. Trial Conduct

### 1. Trial Design

Except for pilot or estimation trials, clinical trial protocols will be hypothesis-driven to assess safety, efficacy and/or pharmacokinetic or pharmacodynamic indices of MSD or comparator products. Alternatively, MSD may conduct outcomes research trials, trials to assess or validate various endpoint measures, or trials to determine patient preferences, etc.

The design (i.e., participant population, duration, statistical power) must be adequate to address the specific purpose of the trial and shall respect the data protection rights of all participants, trial site staff and, where applicable, third parties. All trial protocols are and will be assessed for the need and capability to enroll underrepresented groups. Participants must meet protocol entry criteria to be enrolled in the trial.

## 2. Site Selection

MSD's clinical trials are conducted globally in many different countries and in diverse populations, including people of varying age, race, ethnicity, gender, and accounting for other potential disease related factors. MSD selects investigative sites based on medical expertise, access to appropriate participants, adequacy of facilities and staff, previous performance in clinical trials, as well as budgetary considerations. Prior to trial initiation, sites are evaluated by MSD personnel (or individuals acting on behalf of MSD) to assess the ability to successfully conduct the trial.

PROTOCOL/AMENDMENT NO.: 002-01

Where appropriate, and in accordance with regulatory authority guidance, MSD will make concerted efforts to raise awareness of clinical trial opportunities in various communities. MSD will seek to engage underrepresented groups and those disproportionately impacted by the disease under study. MSD will support clinical trial investigators to enroll underrepresented groups and expand access to those who will ultimately use the products under investigation.

#### 3. Site Monitoring/Scientific Integrity

Investigative trial sites are monitored to assess compliance with the trial protocol and Good Clinical Practice (GCP). MSD reviews clinical data for accuracy, completeness, and consistency. Data are verified versus source documentation according to standard operating procedures. Per MSD policies and procedures, if potential fraud, scientific/research misconduct, privacy incidents/breaches or Clinical Trial-related Significant Quality Issues are reported, such matters are investigated. When necessary, appropriate corrective and/or preventative actions are defined and regulatory authorities and/or ethics review committees are notified

#### **B. Publication and Authorship**

Regardless of trial outcome, MSD commits to publish the primary and secondary results of its registered trials of marketed products in which treatment is assigned, according to the pre-specified plans for data analysis. To the extent scientifically appropriate, MSD seeks to publish the results of other analyses it conducts that are important to patients, physicians, and payers. Some early phase or pilot trials are intended to be hypothesis-generating rather than hypothesis testing; in such cases, publication of results may not be appropriate since the trial may be underpowered and the analyses complicated by statistical issues such as multiplicity.

MSD's policy on authorship is consistent with the recommendations published by the International Committee of Medical Journal Editors (ICMJE). In summary, authorship should reflect significant contribution to the design and conduct of the trial, performance or interpretation of the analysis, and/or writing of the manuscript. All named authors must be able to defend the trial results and conclusions. MSD funding of a trial will be acknowledged in publications.

